6.12 Efficacy Assessments

6.12.1 Epworth Sleepiness Scale (ESS)

The ESS is a self-administered questionnaire with 8 questions asking the subject how likely they would be to doze off or fall asleep in different situations (Appendix 7). Responses range from 0 = would never doze to 3 = high chance of dozing. Subjects will be asked to complete the ESS with regard to the level of sleepiness they experienced over the past 7 days at end of the Stable-Dose Period (Visit 15) and at the end of the Double-Blind Randomized-Withdrawal Period (Visit 16) or Early Termination from the Double-Blind Period. The ESS provides a measure of a person's general level of daytime sleepiness, or their average sleep propensity in daily life. It is a validated measure with high specificity and sensitivity for assessing subjective sleepiness (Johns 1991, Johns 2000, Broderick et al. 2013).

6.12.2 Clinician Global Impression of Severity (CGIs) for Narcolepsy Overall

The CGIs is a 7-point Likert-type rating scale and a widely used assessment in clinical psychopharmacology trials to assess severity of illness (Appendix 8). The responses of this investigator-completed scale range from 1 = normal, no signs of illness to 7 = among the most extremely ill subjects. The Investigator, as a trained rater, will rate his/her impression of the severity of the subject's narcolepsy overall at the end of the Stable-Dose Phase (Visit 15) relative to his/her experience with this patient population.

6.12.3 Clinical Global Impression of Change (CGIc) for Narcolepsy Overall

The CGIc is a 7-point Likert-type rating scale and a widely used assessment to assess efficacy in clinical drug trials. At the end of the Double-Blind Randomized-Withdrawal Period (Visit 16), Investigators as trained raters will rate their impression of any change in the severity of the subject's narcolepsy overall (Appendix 9) since the start of the Double-Blind Randomized-Withdrawal Period (i.e., since the last visit [Visit 15 end of the Stable-Dose Period]) on a 7-point scale ranging from 1 = "very much improved" to 7 = "very much worse." If the subject discontinues during the Double-Blind Randomized-Withdrawal Period, the Investigator as a trained rater will complete the CGIc for narcolepsy overall at Early Termination (Visit 16).

6.12.4 Patient Global Impression of Change (PGIc) for Narcolepsy Overall

The PGIc is a 7-point Likert-type rating scale and a widely used assessment to assess efficacy in clinical drug trials. At the end of the Double-Blind Randomized-Withdrawal Period (Visit 16 or Early Termination), subjects will rate the change in their condition on a 7-point scale ranging from 1 = "very much better" to 7 = "very much worse' since the last visit (Visit 15 [end of the Stable-Dose Period]) (Appendix 10). If the subject discontinues during the Double-Blind Randomized-Withdrawal Period, the subject will complete the PGIc for narcolepsy overall at Early Termination (Visit 16).

Confidential Page 58 of 148

Jazz Pharmaceuticals

6.12.5 36-Item Short Form Health Survey Version 2 (SF-36v2)

The SF-36v2 is a multi-purpose, short-form health survey with 36 questions. It yields an 8 scale profile of functional health and well-being scores as well as psychometrically-based physical and mental health summary measures and a preference-based health utility index (Hays & Stewart 1992, Ware & Sherbourne 1992). Subjects will complete the SF-36v2 with a one-week recall period at the end of the Stable-Dose Period (Visit 15), the end of the Double-Blind Randomized-Withdrawal Period (Visit 16), or Early Termination from the Double-Blind Period (Appendix 11).

6.12.6 European Quality of Life 5 Dimensions 5 Levels (EuroQol/EQ-5D-5L)

The EQ-5D-5L is a standardized instrument for use as a measure of health outcome that includes a descriptive system consisting of 5 dimensions (mobility, self-care, usual activities, pain/discomfort, and anxiety/depression) and an EO visual analogue scale (EuroOol User Guide 2013). It is applicable to a wide range of health conditions and treatments, it provides a simple descriptive profile and a single index value for health status. The EQ-5D-5L includes five levels of severity for each of the 5 dimensions of the descriptive system and was developed to improve the instrument's reliability and sensitivity and to reduce ceiling effects. Subjects will complete the EQ-5D-5L at the end of the Stable-Dose Period (Visit 15), the end of the Double-Blind Randomized-Withdrawal Period (Visit 16), or Early Termination from the Double-Blind Period (Appendix 12).

6.12.7 Cataplexy Frequency Diary

Subjects will complete a daily Cataplexy Frequency Diary (Appendix 13) each night prior to bedtime, to record the number of cataplexy attacks that they had each day beginning at Visit 2 through the end of the Double-Blind Randomized-Withdrawal Period. Subjects must have completed the Cataplexy Frequency Diary on at least 10 out of the 14 days in the Stable-Dose Period occurring prior to the start of the Double-Blind Randomized-Withdrawal Period, or they will be discontinued from the study.

The study staff will review the diary at each study visit and discuss it with the subject at each phone contact.

> Confidential Page 59 of 148

Jazz Pharmaceuticals

6.13 Adverse Event Reporting

6.13.1 Adverse Events (AEs)

An AE is any untoward medical occurrence associated with the use of a drug in humans, whether or not considered related to study drug or procedure.

Adverse events include, but are not limited to: (1) a worsening or change in nature, severity, or frequency of conditions present at the start of the study (defined as Visit 1 and Visit 18 [Re-entry Subjects]); (2) subject deterioration due to primary illness; (3) intercurrent illness; (4) drug interaction; and/or (5) abnormal clinically significant laboratory values.

- Symptoms of the underlying medical condition narcolepsy are not considered as AEs unless there is an exacerbation of the subject's baseline symptoms at entry into the study. (Visit 1 and Visit 18 [subjects who re-enter the study for the Open-Label Extension]).
- Clinically significant adverse changes from baseline clinical status (Visit 1 and Visit 18 [subjects who re-enter the study for the Open-Label Extension]) in ECGs, routine laboratory tests, and physical examinations are considered AEs. Any subject complaint associated with such an abnormal finding will also be reported as an AE.

All AEs, whether observed by the Investigator, reported by the subject, determined from laboratory findings, or other means, will be documented.

For Re-entry Subjects (completed the Main Study), any new clinically significant condition not previously recorded as an AE during the Main Study and which occurred prior to obtaining informed consent for the Open-Label Extension, is considered medical history and should be documented as such (see Section 6.3).

Subjects should be questioned in a general way, without asking about the occurrence of any specific symptom. The Investigator should attempt to establish a diagnosis of the event based on signs, symptoms, and/or other clinical information. In such cases, the diagnosis, not the individual signs/symptoms, should be documented as the AE.

Following questioning and evaluation, all AEs, whether believed by the Investigator to be related or unrelated to the study drug or procedure, must be documented in the subject's medical records, in accordance with the Investigator's normal clinical practice. Each AE is to be evaluated for duration, severity (Section 6.13.2), seriousness (Section 6.13.3), and causal relationship to the study drug or procedure (see Section 6.13.4).

> Confidential Page 60 of 148

6.13.2 Severity Assessment

Adverse events will be classified by the Investigator as mild, moderate, severe, life-threatening or fatal, as defined below. When the severity of the AE changes over time, the change in severity will be recorded on the AE eCRF as a new AE, and the original AE will stop when the new AE starts

Table 5 Adverse Event Severity Definitions

Classification	Definition
Mild	Mild; asymptomatic or mild symptoms; clinical or diagnostic observations only; intervention not indicated
Moderate	Moderate; minimal, local or noninvasive intervention indicated; limiting age-appropriate instrumental ADL^a
Severe	Severe or medically significant but not immediately life-threatening; hospitalization or prolongation of hospitalization indicated; disabling; limiting age-appropriate self-care $\mathrm{ADL}^{\mathrm{b}}$
Life-threatening	Life-threatening consequences; urgent intervention indicated
Death	Death related to AE

^a Instrumental ADL refers to preparing meals, shopping for groceries or clothes, using the telephone, managing money, etc.

ADL = activities of daily living; AE = adverse event.

Source: CTCAE, Version [4.03].

6.13.3 Serious Adverse Events (SAEs)

Serious adverse events (SAEs) must be reported to Jazz Pharmaceuticals or its designee using the SAE Reporting form within 24 hours of first knowledge of the event by study personnel. SAE Reporting forms and contact information will be provided to the study site. The event must also be entered on the AE eCRF in accordance with the eCRF Completion Guidelines.

An SAE is an AE that fulfills any of the following criteria:

- Is fatal (results in death)
- Is life-threatening (Note: the term "life-threatening" refers to an event in which the subject was at immediate risk of death at the time of the event; it does not refer to an event that could hypothetically have caused death had it been more severe)
- Requires in-patient hospitalization or prolongs existing hospitalization
- Results in persistent or significant incapacity or disability, defined as substantial disruption of the ability to conduct normal life functions
- Is a congenital anomaly/birth defect

Confidential Page 61 of 148

Jazz Pharmaceuticals

b Self-care ADL refers to bathing, dressing and undressing, feeding self, using the toilet, taking medications, and not bedridden A Semi-colon indicates 'or' within the description of the grade.

- Is an important medical event
- Important medical events that may not result in death, be life-threatening, or require
 hospitalization may be considered an SAE when, based on appropriate medical
 judgment, they may jeopardize the subject and may require medical or surgical
 intervention to prevent one of the outcomes listed above in the definition of an SAE.

Jazz Pharmaceuticals

- Examples of such medical events include allergic bronchospasm requiring intensive treatment in an emergency room or at home, blood dyscrasias or convulsions that do not result in in-patient hospitalization, the development of drug dependency or drug abuse, and the occurrence of suicidal ideation.
- Additionally, any suspected transmission of an infectious agent via a medicinal product should be reported as an important medical event.

A hospitalization is NOT considered an SAE if:

- It is planned prior to subject entering trial or prior to entrance of Open-Label Extension (only if subject is re-entering, i.e., completed the main study)
- It is for social reasons and respite care in the absence of any deterioration in the subject's general condition
- It is elective in nature and not related to worsening of an underlying condition

Complications that occur during hospitalizations are AEs. If a complication prolongs the hospitalization, it is an SAE.

"In-patient hospitalization" means the subject has been formally admitted to a hospital for medical reasons, for any length of time. Emergency room care without admission to a hospital is considered outpatient care.

Overdose, medication errors, and drug misuse of the study drug are SAEs only if any of the seriousness criteria are met

The SAE Reporting Form must be completed as thoroughly as possible before transmittal to the contact provided on the form. The Investigator should provide his/her assessment of the causality (relationship) to study drug and procedure at the time of the report. Where the Investigator does not provide causality assessment of the SAE at the time of the initial report, the event by default will be presumed "Related." If the Investigator's assessment of causality changes, then a follow-up SAE Reporting forms must be submitted.

Confidential Page 62 of 148

6.13.4 Causal Relationship to Study Drug or Procedure

The Investigator's assessment of an AE's relationship to study drug and to study procedures is required. The relationship or association of the study drug or procedure in causing or contributing to the AE will be characterized using the following classification and criteria:

Related or	There is a reasonable possibility that the study drug or procedure caused the
Suspected	event—i.e., there is evidence to suggest a causal relationship between the study
to be	drug or procedure and the AE.
Related to Study Drug or Procedure	Some temporal relationship exists between the event and the administration of the study drug or procedure and the event is unlikely to be explained by the subject's medical condition, other therapies, or accident.
	The event follows a reasonable temporal sequence from administration of the study drug or procedure and at least one of the following instances of clinical evidence:
	 The event follows a known or suspected response pattern to the study drug or procedure.
	 The event improves upon stopping the study drug or procedure or decreasing the dose (positive dechallenge).
	 The event reappears upon repeated exposure, if medically appropriate (positive rechallenge).
Not Related to Study Drug or Procedure	There is not a reasonable possibility or clinical evidence that the study drug or procedure caused the event.
	The event can be readily explained by other factors such as the subject's underlying medical conditions, concomitant therapy, or accident; or there is no temporal relationship between study drug or procedure and the event.

6.13.5 Other Immediately Reportable Experiences

The following immediately reportable experiences may occur during participation in this clinical trial and must be reported within 24 hours of first knowledge of the event by study personnel to the appropriate Jazz Pharmaceuticals contact or designee:

- Alanine aminotransferase (ALT) or aspartate aminotransferase (AST) with a 3-fold or greater elevation above the upper limit of normal (ULN) in addition to an elevation of serum total bilirubin greater than two times the ULN, with no other identifiable etiology
- Liver enzyme (AST, ALT) value greater than or equal to 5 times the ULN

As with SAEs (Section 6.13.3), the immediately reportable experiences noted above must be reported on the SAE Reporting form, which should be completed as thoroughly as possible before transmittal to the contact provided on the form. The Investigator must provide his/her assessment of causality to study drug or procedure at the time of the initial report. These experiences must also be entered as AEs on the AE eCRF in accordance with the eCRF Completion Guidelines. See Section 6.13.8 for details related to reporting an immediately reportable experience of pregnancy.

Confidential Page 63 of 148

Jazz Pharmaceuticals

6.13.6 Adverse Events and Serious Adverse Event Recording and Reporting Timeframe

The Investigator must document all AEs and SAEs that occur during both the Main Study and the Open-Label Extension until the Final Study Visit or Early termination, regardless of their relationship to study drug or procedure. For those subjects who participate in the Main Study only and for Rollover Subject (progress directly into the Open-Label Extension), all AEs and SAEs will be documented from the time written informed consent is obtained at Visit 1. For Re-entry Subjects (complete the Main Study), all AEs and SAEs for the Open-Label Extension will be documented from the time written informed consent is obtained at Visit 18.

SAEs and immediately reportable experiences must be reported within 24 hours of first knowledge of the event by study personnel as described in Section 6.13.3 and Section 6.13.5.

If an Investigator becomes aware of an SAE within 30 days after the last dose of study drug, the event must be documented and reported as described in Section 6.13.3.

Any SAE assessed as related to study drug or procedure by the Investigator must be reported regardless of time after study termination.

Follow-up of Adverse Events and Serious Adverse Events 6.13.7

Adverse events assessed as not related to study drug or procedure, including clinically significant laboratory tests, ECGs, or physical examination findings, must be followed until the event resolves, the condition stabilizes, the event is otherwise explained, or the Final Study Visit occurs, whichever comes first.

AEs and SAEs assessed as related to study drug or procedure will be followed for as long as necessary to adequately evaluate the subject's safety, or until the event stabilizes, or the subject is lost to follow up. The outcome at the time of the Final Study Visit should be documented. If resolved, a resolution date should be provided, and for SAEs, a follow-up SAE Report form should be submitted indicating the resolution date.

The Investigator is responsible for ensuring that follow-up includes any supplemental investigations indicated to elucidate the nature and/or causality of the AE. This may include additional clinical laboratory testing or investigations, examinations, histopathological examinations, or consultation with other health care professionals as is practical.

> Confidential Page 64 of 148

6.13.8 Pregnancy

Pregnancy of a subject or a male subject's partner is an immediately reportable experience and should be reported within 24 hours of first knowledge of the event by study personnel to the appropriate Jazz Pharmaceuticals contact or designee. If a subject or a male subject's partner becomes pregnant any time after the first dose of study drug is taken until 90 days after the last dose of study drug is taken, the pregnancy form should be used to report the pregnancy to Jazz Pharmaceuticals or its designee. The pregnancy of a subject or a male subject's partner should be followed until the outcome of the pregnancy is known, and in the case of a live birth, for 6 months following the birth of the child. The infant follow-up form should be used to report information regarding the status of the infant.

6.13.9 Emergency Unblinding

A subject's treatment assignment should only be unblinded when knowledge of the treatment is necessary for immediate medical management of the subject. In the case of an immediate medical emergency, an Investigator or his/her designee will be able to unblind a subject at any time via the IWRS. Every attempt should be made to contact Jazz Pharmaceuticals or its designee before unblinding a subject as long as this does not compromise the safety of the subject. If a request for unblinding is received from an Investigator, the Medical Monitor will discuss with the Investigator the rationale for the request. A comment must be entered in the source documentation to specify the reason for unblinding, along with the date on which the code was broken and the identity of the person authorizing the unblinding. Subjects for whom the blind is broken will be withdrawn from the study.

6.13.10 Regulatory Reporting

Jazz Pharmaceuticals or its designee is responsible for reporting relevant SAEs to the relevant regulatory authorities, concerned central ethics committees (CECs) and participating Investigators, in accordance with ICH guidelines, the US Code of Federal Regulations (CFR), the EU Clinical Trial Directive (2001/20/EC) and/or local regulatory requirements.

The reference safety information for the determination of expectedness for JZP-258 oral solution is in the Investigator's Brochure.

Suspected unexpected serious adverse reactions (SUSARs) that are fatal or life-threatening will be reported to the relevant regulatory authorities, CECs, and participating Investigators no later than 7 days after knowledge of such a case, and relevant follow-up information provided within an additional 8 days. All other SUSARs (i.e., non-fatal or non-life-threatening) will be reported to the relevant regulatory authorities, CECs, and all participating Investigators no later than 15 days after first knowledge of the event.

Once a year throughout the study, a report listing of all SUSARs (and SAEs if required by local regulation) that have occurred during the period and a report of the subject's safety will be submitted to the applicable authorities and CECs.

Confidential Page 65 of 148

The subject's treatment assignment may be unblinded for regulatory reporting purposes. Notification of the treatment assignment is only made known to those who require it for safety reporting and submission processes. All other individuals involved in the study, including the Investigator, will remain blinded to treatment assignment. Subjects for whom the blind is broken for this reason will not be withdrawn from the study.

Reporting of SAEs by the Investigator to his or her local ethics committee will be done in accordance with the standard operations procedures and policies of the ethics committee. Adequate documentation must be maintained showing that the ethics committee was properly notified

6.14 Removal of Subjects from the Trial or Study Drug

6.14.1 Reasons for Early Terminations

All subjects are free to withdraw from participation in this study at any time, for any reason, and without prejudice. The Investigator must withdraw any subject from the study if the subject states that he/she wants to stop participating in the study.

The Investigator, Jazz Pharmaceuticals or its designee may remove a subject from the study at any time and for any reason.

If any of the criteria below are met during the study, study drug administration must be stopped and the subject discontinued from the study.

- Suicide risk reported or assessed by C-SSRS
- 3-fold or greater elevation above the ULN of ALT or AST accompanied by an elevation of serum total bilirubin greater than two times the ULN
- Liver enzyme (AST, ALT) value greater than or equal to 5 times the ULN
- Creatinine > 176 μmol/L
- Positive alcohol screen
- Positive urine drug screen
- Positive pregnancy test

For all subjects who prematurely discontinue from the Main Study, an attempt should be made to perform all early termination assessments (same assessments as those performed at the final study visit). Subjects should be asked to return 2 weeks later for a safety follow-up visit.

The specific reason for the discontinuation should be documented on the termination eCRF. If a subject withdraws informed consent, the specific reason for withdrawing the informed consent should be stated.

Adverse events resulting in termination will be followed to the satisfactory resolution and determination of outcome as ascertained by the Investigator (and/or Jazz Pharmaceuticals or its designee). The data will be recorded on the appropriate eCRF.

Confidential Page 66 of 148

P-258 Jazz Pharmaceuticals

For all subjects who prematurely discontinue from the Open-Label Extension, an attempt should be made to perform all early termination assessments (same assessments as those performed at the final study visit). Subjects should be asked to return 2 weeks later for a safety follow-up visit.

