6.10 Clinical Laboratory Tests

6.10.1 **Laboratory Parameters**

Subjects will be in a seated or supine position during blood collection. Clinical laboratory tests will include the following as listed in Table 3. Clinical laboratory tests will be performed at the times indicated in Appendix 1.

> Confidential Page 54 of 148

JZP-258 Jazz Pharmaceuticals

Clinical Trial Protocol: 15-006 Amendment 5

Table 3 List of Laboratory Tests

Hematology:

Complete blood count (CBC), including platelet count and white blood cell count (WBC) with differential

Urinalysis:

- Appearance
- Bilirubin
- Color
- Glucose
- Ketones
- Nitrite
- Occult blood
- pН
- Protein
- Specific gravity
- Urobilinogen
- *Pregnancy Screen: Serum at screening

Urine at start of Titration Period

Drug Screen (urine) Alcohol Screen

Serum Chemistry:

- Albumin (ALB)
- Alkaline phosphatase (ALK-P)
- Alanine aminotransferase (ALT; SGPT)
- Aspartate aminotransferase (AST; SGOT)
- Blood urea nitrogen (BUN)
- Calcium (Ca)**
- Chloride (Cl)
- Creatinine
- Creatine kinase
- Gamma-glutamyl transferase (GGT)
- Globulin
- Glucose
- Lactate dehydrogenase (LDH)
- Phosphorus
- Potassium (K)**
- Sodium (Na)**
- Magnesium**
- Total bilirubin
- Direct bilirubin
- Total cholesterol
- Total protein
- Triglycerides
- Uric acid
- Thyroid stimulating hormone (TSH)(screening only)

With the exception of the urine pregnancy test done on site, the clinical laboratory tests scheduled for this study will be performed at a central laboratory. An authorized local laboratory, as indicated on the Form FDA 1572 or equivalent, may be used if necessary as an emergency laboratory. The Investigator will supply Jazz Pharmaceuticals or its designee with the local laboratory's current licensure and laboratory reference ranges.

Please note exclusionary clinical laboratory parameters listed in the exclusion criteria. In addition, any laboratory parameter that is out-of-range and considered clinically significant (as determined by the Investigator) at the end of treatment must be re-evaluated. The Investigator will provide an explanation of all clinically significant observations; clinically significant adverse changes from baseline clinical status must be reported as AEs (see Section 6.13.1).

Confidential Page 55 of 148

[figure not shown]

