6.10.2 Sample Collection, Storage, and Shipping

The laboratory will supply detailed instructions and all containers for blood and urine investigations. Blood and urine sample volumes will meet the laboratory's specifications. The actual time of blood collection for all samples will be recorded.

Blood samples for hematology, serum chemistry, and urinalysis will be collected while the subject is fasting during the Screening Period, and at the end of the Double-Blind Period or Early Termination for the Main Study and during Visit 18 (only subjects who are re-entering) and Visit 33 (or at Early Termination).

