Visits 4, 5, 7, 8, 9, and 11

- Record all AEs that occurred since the last visit or phone contact on the AE eCRF.
- Record all concomitant medications that were taken since the last visit or phone contact on the concomitant medications eCRF.
- Administer the PHQ-9 (Weeks 2, and 6 only).
- Discuss the frequency of cataplexy attacks with the subject and confirm that the Cataplexy Frequency Diary is being completed.
- Discuss dosing with the subject and confirm compliance; confirm that the Dosing Diary is being completed.
- Discuss tapering of anticataplectics with the subject (Groups 2 and 3 only).
- Assess control of cataplexy, EDS and tolerability to current dose.
 - All Pre-randomization Groups: If needed, continue titration of JZP-258 and provide instructions for dosing (titration up or down or staying on the current dose) until the next phone contact or clinic visit. JZP-258 dose adjustments are not allowed after Week 10.
 - Pre-randomization Groups 2 and 3: If further JZP-258 titration is not needed and the subject has remained on the same JZP-258 dose for the previous 2 weeks begin taper of the non-indicated anticataplectic.
 - Pre-randomization Groups 2 and 3: When taper of non-Xyrem anticataplectic is initiated, assess taper progress and advise subject on taper instructions, as appropriate.
 Anticataplectic taper must be completed by Week 10.
- Schedule the next phone contact or clinic visit.

CLINIC VISITS - END OF WEEK 4 AND 8 - VISITS 6 AND 10

- Obtain weight in ordinary indoor clothes (without shoes).
- Obtain vital signs (systolic and diastolic blood pressure, heart rate and respiratory rate, and body temperature), in the seated position after the subject has been resting for 5 minutes.
- Obtain a blood sample for electrolytes (Na, K, Ca, and Mg).
- Obtain a urine pregnancy test for all females of childbearing potential (Section 6.10.1).
- Perform alcohol screen and urine drug screen.
- Record all AEs that occurred since the last phone contact on the AE eCRF.
- Record all concomitant medications that were taken since the last phone contact on the concomitant medications eCRF.
- Administer:
 - C-SSRS Since Last Visit version.

Confidential Page 72 of 148

- PHO-9.
- Review Cataplexy Frequency Diary for completeness.
- Review the Dosing Diary for compliance with dosing.
- Assess control of cataplexy, EDS and tolerability to current dose.

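### Hepatic and creatinine stopping criteria apply throughout the study, but no serum chemistry is planned between first dose and Visit 16, or between extension entry and Visit 33

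*Protocol*

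**What the plan says.** Protocol Section 6.14.1: "If any of the criteria below are met during the study, study drug administration must be stopped". Such a subject also leaves the study. Three items in that list rest on serum chemistry. One combines a raised ALT or AST with raised total bilirubin. A second is "Liver enzyme (AST, ALT) value greater than or equal to 5 times the ULN". The third is a renal limit, "Creatinine > 176" (in μmol/L). The remaining items are suicide risk, a positive alcohol or urine drug screen, and a positive pregnancy test.

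Table 3 in Section 6.10.1 places ALT, AST, total bilirubin and creatinine in the serum chemistry panel. Section 6.10.2 fixes when that panel is taken: "Blood samples for hematology, serum chemistry, and urinalysis will be collected while the subject is fasting during the Screening Period". The other time points it names are Visit 16 or early termination in the Main Study, Visit 18 for re-entry subjects, and Visit 33 or early termination in the extension. The visit lists for Visits 2, 6, 10, 14 and 15 contain only the instruction "Obtain a blood sample for electrolytes (Na, K, Ca, and Mg"). Visits 19 and 30 in the extension have the same instruction.

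SAP 9.9.2 gives the same time points for non-electrolyte chemistry: Main Study baseline, end of the randomized-withdrawal period, extension baseline and end of extension. SAP 9.9 excludes data collected on placebo from the safety summaries that run across all study periods.

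**The concern.** A mandatory stopping criterion implies that someone will look at the quantity it depends on. Here the planned schedule measures these quantities before dosing starts and again when the dosing period ends. A site that follows the protocol exactly gets no ALT, AST, bilirubin or creatinine result in between on which to act.

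The same schedule limits the safety dataset. Safety is a stated secondary objective. A placebo-arm completer takes JZP-258 for 14 weeks, but the only post-baseline Main Study chemistry is taken after two further weeks on placebo. Any drug-related shift that had reversed by then is not seen. One that persisted would be recorded as an on-placebo value.

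**Working it through.** **Plan's own figure.** Main Study treatment is 12 + 2 + 2 = 16 weeks (synopsis, Duration of Treatment). With the extension it is 16 + 24 = 40 weeks. Both agree with the protocol.

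**Planned blood draws against the stopping analytes** (Sections 7.1.1 to 7.2.3, Appendix 1.1 and 1.2):

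| Visit | Time | Planned blood | ALT, AST, bilirubin, creatinine? |
|---|---|---|---|
| 1 | Day −30 to −1 | Full chemistry | Yes, before dosing |
| 2 | Day 1 | Electrolytes | No (also before dosing) |
| 6, 10, 14, 15 | Weeks 4, 8, 12, 14 | Electrolytes | No |
| 16 or early termination | Week 16 | Full chemistry | Yes, as Main Study dosing ends |
| 18 (re-entry) | Extension screening | Full chemistry | Yes, before extension dosing |
| 19 (re-entry) | Extension Day 1 | Electrolytes | No (also before dosing) |
| 30 | Extension Week 12 | Electrolytes | No |
| 33 or early termination | Extension Week 24 | Full chemistry | Yes, as extension dosing ends |

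Between first dose and Visit 16 there are four planned post-dose draws, and none measures the stopping analytes. Between extension entry and Visit 33 there is one such draw, also without them. SAP 6.3, Table 2, agrees: chemistry has no analysis window in the titration or stable-dose periods.

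**Length of the interval.** Visit 1 to Visit 16 can span 30 + 112 = 142 days (20.3 weeks), or 44 + 112 = 156 days (22.3 weeks) with the two-week screening extension. These spans include 30 or 44 days before any study drug. The dosing interval is 112 days, or 16 weeks. The extension interval is 24 weeks.

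**Comparison within the same list.** C-SSRS, alcohol screen, urine drug screen and urine pregnancy test are scheduled at Visits 2, 6, 10, 14, 15 and 16, and also at Visit 3 when it is a clinic visit. In the Main Study the gap is specific to the hepatic and creatinine items.

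**Placebo arm.** JZP-258 exposure before withdrawal is 12 + 2 = 14 weeks, followed by 2 weeks of placebo. The planned share is 65 / 130 = 50% of randomized subjects. Their Visit 16 chemistry is collected on placebo, so SAP 9.9 removes it from the across-period summaries. It remains in the by-treatment summaries of the randomized-withdrawal period, as a placebo value.

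**The case against.** Section 6.14.1 is conditional. It does not promise periodic testing, and how often to sample chemistry is a design choice on which protocol and SAP agree. The documents also give no reason to expect a liver or kidney signal. Neither Table 2 of the protocol nor the postmarketing list in Section 1.3.6 contains a hepatic or renal laboratory reaction, and Section 1.4.2 reports no clinically significant laboratory trends. That stands, and it limits how serious the point is. It does not supply a planned check.

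Several stronger readings are tempting but not supported:

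- A reader might infer that the criteria cannot operate. They can. The protocol allows unscheduled visits at any time (Section 7.1), an emergency local laboratory (6.10.1) and additional laboratory testing to follow up adverse events (6.13.7). For a rollover subject, Visit 16 is also extension Day 1, so its result can stop extension dosing. An early-termination sample is planned too, but it follows the decision to stop.
- A reader might infer that the 24-hour reporting duty in Section 6.13.5 fails. It does not: it applies to any value that becomes known, including one from Visit 16 or Visit 33.
- A reader might infer that rollover subjects restart drug before the Visit 16 result is known. Drug is dispensed that day and samples go to a central laboratory, but the documents give no turnaround time, and subjects from the JZP-258 arm are not restarting.
- A reader might infer that placebo-arm subjects never give an on-drug value. Those who enter the extension may give one at Visit 33. Nor is the JZP-258 arm the only Main Study source: early terminators are asked to complete Visit 16 assessments, and the plan expects about 185 − 130 = 55 losses before randomization, all from open-label JZP-258.
- A reader might infer that extra tests at Visits 2 and 19 would help. Both are pre-dose draws and cannot detect an on-drug event.

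**Conclusion.** The point holds for planned sampling. For 16 weeks in the Main Study and 24 weeks in the extension, a mandatory stopping rule has no planned measurement behind its hepatic and creatinine items and depends on discretionary testing. Separately, placebo-arm completers (planned 65 of 130) provide no planned on-JZP-258 liver or renal value from the Main Study.

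This rests on three assumptions: sites follow Appendix 1 as written, the planned 65 per arm are randomized, and a Visit 16 sample in the placebo arm counts as collected on placebo under SAP 9.9. The efficacy analysis is unaffected. The change is worth making because the mismatch concerns a mandatory rule, not because the documents point to an expected hepatic or renal effect.

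**What to change.** Reconcile Section 6.14.1 with Section 6.10.2, Appendix 1 and SAP 9.9.2. Either the planned laboratory schedule should support the stated criteria, or the protocol should say that between the chemistry visits they rely on unscheduled testing, and justify that. Sampling frequency and thresholds are for the sponsor to decide. The same edit should align the creatinine bound, which is strictly above 176 in Section 6.14.1 and at or above 176 in the SAP 9.9.2 listing.

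For the safety dataset, one option is to report the existing chemistry analytes on post-dose blood already drawn for electrolytes before randomization, for example at Visit 15. That would give an on-JZP-258 value for both arms. SAP 9.9.2 and Table 2 would then need the added time point.

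The costs are laboratory charges, follow-up of incidental abnormal values, a wording change to the fasting requirement in Section 6.10.2, and confirmation from the laboratory that sample volume and tube type are adequate. If they are, no extra visit or blood draw is needed.
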